5.1.10.3 Hepatobiliary

In case of abnormal liver tests or signs and symptoms suggestive of drug-induced liver injury, subjects will be closely observed, liver tests will be repeated, and ponesimod may need to be prematurely discontinued or interrupted.

The central laboratory will send alerts to the principal investigator and the sponsor whenever any of the following hepatobiliary laboratory abnormalities are recorded during the study:

- \geq Grade 2 elevation ALT ($> 3 \times \text{ULN}$)
- \geq Grade 2 elevation AST ($> 3 \times \text{ULN}$)
- \geq Grade 2 elevation blood bilirubin (same as TBL) ($> 1.5 \times \text{ULN}$)

The site will immediately contact the subject and ask him/her to return to the site within 72 hours, at the latest, to repeat the test by the central laboratory (unless the clinical situation mandates immediate local testing). An inquiry should be made about symptoms.

Should repeat testing confirm continuing abnormality, the following will apply:

Ponesimod must be prematurely discontinued for any of the following:

- Grade 4 ALT or AST elevation ($> 20.0 \times \text{ULN}$).
- Grade 4 blood bilirubin (same as TBL) elevation ($> 10.0 \times \text{ULN}$).
- Grade 2 or higher ALT or AST elevation ($> 3 \times \text{ULN}$) and (TBL $> 2 \times \text{ULN}$ or international normalized ratio [INR] > 1.5 ; corresponds to Hy's Law).
- Grade 2 or higher ALT or AST elevation ($> 3 \times \text{ULN}$) with the appearance of: fatigue, nausea, vomiting, right upper quadrant pain or tenderness, fever, rash, and/or eosinophilia ($> 5\%$).
- Grade 3 or higher ALT or AST elevation ($> 5.0 \times \text{ULN}$) during study Days 2–56 or study Days 149–168.
- Grade 3 or higher TBL elevation ($> 3.0 \times \text{ULN}$) during study Days 2–56 or study Days 149–168.
- Grade 3 or higher ALT or AST elevation ($> 5.0 \times \text{ULN}$) and subject is taking ponesimod 5 mg.
- Grade 3 or higher TBL elevation ($> 3.0 \times \text{ULN}$) and subject is taking ponesimod 5 mg.

Please see box “Monitoring for all subjects with confirmed \geq grade 2 AST, ALT, or TBL elevations”.

Confidential

Ponesimod is interrupted for any of the following:

- Grade 3 ALT or AST elevation ($> 5.0\text{--}20.0 \times \text{ULN}$) during study Days 57–148 or during the Extension Treatment Period.
- Grade 3 TBL elevation ($> 3.0\text{--}10.0 \times \text{ULN}$) during study Days 57–148 or during the Extension Treatment Period.

Procedure for interruption

- Interrupt ponesimod for at least 7 days.
- Perform a re-test of AST, ALT, TBL within 7 days.
- If elevated values do not return to baseline levels within 7 days following treatment interruption, **ponesimod is prematurely discontinued. Please see box “Monitoring for all subjects with confirmed \geq grade 2 AST, ALT, or TBL elevations”.**
- If elevated values return to baseline levels within 7 days following treatment interruption, **ponesimod is re-initiated with up-titration.**

Procedure for re-initiation with up-titration

- Re-initiation occurs 8–10 days after ponesimod was interrupted.
- The previously tolerated dose is targeted at re-initiation with up-titration. For subjects on ponesimod 10 mg at the time of interruption, the 5 mg dose is targeted. For subjects on 20 mg at the time of interruption, the 10 mg dose is targeted. Subjects remain on the lower dose for the remainder of the study, with no further dose-escalation.
- **Re-initiation and up-titration should be conducted in accordance with Section 5.1.8, scenario 4.**

Perform a re-test of AST, ALT, TBL at 5–7 and 10–12 days following re-initiation, and monthly thereafter. Recurrence of \geq grade 3 AST, ALT, TBL results in premature discontinuation with follow-up monitoring.

Please see box “Monitoring for all subjects with confirmed \geq grade 2 AST, ALT, or TBL elevations”.

Confidential

Monitoring for all subjects with confirmed \geq grade 2 AST, ALT, or TBL elevations

- Monitoring continues even after ponesimod discontinuation or interruption.
- AST, ALT, and TBL are re-tested weekly, and more frequently if indicated, until laboratory abnormalities are no longer regarded as clinically relevant.
- Follow-up monitoring, including more frequent visits, is provided until signs and symptoms have resolved or until medically indicated.
- Further diagnostic work-up/consultation with a hepatologist or other specialist should be considered according to local practice and the clinical situation.

Any clinically relevant finding found after ponesimod initiation and during the follow-up period and meeting the definition of an AE will be recorded in the eCRF.

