	Hematology**/Chemistry**/ Urinalysis	X	X pre-dose	X (4) pre-dose /local and central lab	X pre-dose
	Tuberculosis test**	X			
	Viral serology**	X			
	Additional blood samples for exploratory biomarkers**		X		
	Pregnancy test**/ MOC* (5)	X serum**	X serum/urine*	X urine*	X urine*
	PK and PD** sampling		X See Section 7.2.1	X pre-dose	X pre-dose & 3 hr post-dose
	Study drug dispensing & accountability (6)**		X	X	X
	AEs & SAEs (7)*	X	X	X	X

*Data collected in the eCRF **Electronically transferred to the sponsor

Table 1 Visit and assessment schedule (continued)

Periods	Name	Continued: CORE TREATMENT PERIOD, COURSE 3 (20 mg)			UNSCHEDULED Applies to all periods in Table 1	FOLLOW-UP PERIOD 1	
		16 Weeks					
Visits	Number	6	7	8	R1, R2, ...	U1, U2, ...	9, 10
	Name	W16	W20	W24 (EOT1)	Re-initiation	Un-scheduled	FU1, FU2 (8)
	Time	Week 16	Week 20	Week 24 (earlier if prematurely discontinued)	Any day between Day 1 and EOT2	Any day between Day 1 and EOS	EOT1+30 & EOT1+90 days
	Visit window	± 7 days	± 7 days	± 7 days	NA	NA	+ 7 days
Chronic GVHD Activity Assessment, Form A and B*				X			X (9)
Lee Symptom Scale*				X			X (9)
Concomitant medications*		X	X	X	X	X	X
Physical examination*				X		Optional	
Body weight and height*				X (weight only)		Weight optional	
Systolic/diastolic blood pressure*		X pre-dose	X pre-dose	X	X See Section 5.1.7	X pre-dose	X (FU1 only)
12-lead ECG (2)**		X pre-dose	X pre-dose	X	X See Section 5.1.7	Optional; pre-dose	X (FU1 only)
Ophthalmological examination				X		Optional	
OCT (3)				X		Optional	
Spirometry*/DLco*				X		Optional	X (FU1 only)
Hematology**/Chemistry**/Urinalysis		X pre-dose	X pre-dose	X	X pre-dose	Optional	X
Additional blood samples for exploratory biomarkers**				X			X (FU1 only)
Pregnancy test*/MOC* (5)		X urine	X urine	X urine	X urine	Optional urine	X urine
PK and PD** sampling		X pre-dose	X pre-dose	X			X (PD only) (FU1 only)
Study drug dispensing & accountability (6)**		X	X	X	X		
AEs & SAEs (7)*		X	X	X	X	X	X

*Data collected in the eCRF **Electronically transferred to the sponsor

Table 1 Visit and assessment schedule (continued)

Periods	Name	EXTENSION TREATMENT PERIOD				FOLLOW-UP PERIOD 2
		Duration	96 Weeks			
Visits	Number	11	12, 13, 14, 15, 16	17, 18, 19, 20, 21, 22	23	24
	Name	EX-1 (8)	EX-2, 3, 4, 5, 6	EX-7, 8, 9, 10, 11, 12	EX-13	FU3 (EOS) (8)
	Time	EOT1 + 7 days to EOT1 + 90 days (10)	EX-Weeks 4, 8, 12, 16, 20	EX-Weeks 24, 36, 48, 60, 72, 84	EX-Week 96 (EOT2)	EOT2 + 30 days

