8.5.1 Visits for re-initiation of study drug

As described in detail in Section 5.1.8, subjects may need to be monitored at the study site when re-initiating study drug following a study drug treatment interruption.

The following assessments/procedures need to be done during the re-initiation visit:

- Recording of changes in concomitant medications
- Assessing and recording of MOC (for WOCBP only)
- Hematology, blood chemistry (pre-dose)
- SBP/DBP (pre-dose)

Confidential

- SBP/DBP hourly for up to 12 h post-dose (under the responsibility of the cardiac safety assessor) with a minimum of 4 h post-dose.
- 12-lead ECG (pre-dose)
- 12-lead ECG hourly for up to 12 h post-dose (under the responsibility of the cardiac safety assessor) with a minimum of 4 h post-dose.
- Urine pregnancy test for WOCBP (if applicable)
- IRT call and study drug dispensing
- The discharge criteria will be applied as described for Day 1. Subjects may be discharged from the hospital if they meet the discharge criteria before 12 h post-dose but no sooner than 4 h post-dose [see Section 5.1.7]
- Recording of AEs and SAEs.

The date of visit and any data related to study assessments performed during this visit (12-lead ECGs, SBP/DBP) will be reported on the specific eCRF pages for unscheduled visit for re-initiation requiring up-titration of study drug.

These visits for the cardiac monitoring of the subjects when re-initiating study drug are additional unscheduled visits. The regular scheduled study visits must be resumed according to the original visit and assessment schedule. If the visit occurs at the same time as a regular visit, all non-redundant regular visit assessments have to be performed as well.

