8.5.2 Unscheduled visits for reasons other than re-initiation of study drug

Unscheduled visits may be performed at any time during the study for reasons other than re-initiation of study drug. Depending on the reason for the unscheduled visit (e.g., loss of efficacy, AE, etc.), appropriate assessments may be performed based on the judgment of the investigator and must be recorded in the eCRF. After an unscheduled visit, the regular scheduled study visits must continue according to the planned visit and assessment schedule.

Unscheduled visit assessments may include:

- Assessment of concomitant medications
- Assessment of MOC (for WOCBP only)
- PFTs
- SBP/DBP (pre-dose)
- 12-lead ECGs (e.g., in case of need of concomitant treatment with a QT prolonging drug with known risk of Torsades de Pointes [see Appendix 3], pre-dose).
- Ophthalmological examination
- OCT (e.g., presence of visual symptoms suggestive of macular edema)
- Spirometry (under the responsibility of the pulmonologist)

Confidential

- DLCO (under the responsibility of the pulmonologist)
- Physical examination
- Measurement of body weight
- Complete laboratory tests including: hematology, blood chemistry, urinalysis, or serum pregnancy test (for WOCBP only)
- Assessment of AEs and SAEs
- Return of study drug blisters and unused medication and dispensing of new blisters, if appropriate.

Additional unscheduled spirometry will have to be conducted in the event of respiratory symptoms (e.g., dyspnea) during the course of the study. Administration of inhaled short-acting β_2 agonists (e.g., albuterol/salbutamol) for symptom relief may be performed at the discretion of the investigator. Administration of short-acting β_2 agonists will be collected in the eCRF.

If any of the laboratory parameters listed in Section 7.3.11.2 need to be analyzed, this must be done at the central laboratory, except in case of emergency; if it has been done at a local laboratory, results must be recorded in the eCRF [see Section 7.3.11].

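### The liver stopping rule in 5.1.10.3 uses INR, but the weekly on-drug re-tests do not name it, so between scheduled or re-initiation chemistry panels that limb of the rule need not be checked

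*Combined protocol and SAP*

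**What the plan says.** **The stop.** Section 5.1.10.3 makes discontinuation mandatory when a repeat test confirms ALT or AST above 3 x ULN together with TBL above 2 x ULN or "international normalized ratio [INR] > 1.5". The protocol identifies this combination with Hy's Law. Section 5.1.10 applies these criteria in both treatment periods.

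**The repeat after an alert.** Alerts in 5.1.10.3 fire on ALT, AST or bilirubin. The subject returns within 72 hours "to repeat the test by the central laboratory". INR is neither named nor excluded.

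**Weekly monitoring.** For every confirmed Grade 2 or higher elevation, the monitoring box says "AST, ALT, and TBL are re-tested weekly, and more frequently if indicated".

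**After an interruption.** The instruction is "Perform a re-test of AST, ALT, TBL at 5–7 and 10–12 days following re-initiation, and monthly thereafter". A recurrence of at least "grade 3 AST, ALT, TBL results in premature discontinuation with follow-up monitoring".

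**Where INR is required.** INR is part of the clinical chemistry list in 7.3.11.2, drawn at the visits in Table 1. Section 8.5.1 includes blood chemistry under "The following assessments/procedures need to be done during the re-initiation visit". At other unscheduled visits Table 1 marks chemistry as optional, and 8.5.2 introduces its list with "Unscheduled visit assessments may include".

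**The concern.** The stop has two alternative limbs once ALT or AST exceeds 3 x ULN. The bilirubin limb is fed by the weekly re-tests. The INR limb is not, on the wording given. A mandatory stop should rest on a measurement that the protocol also makes mandatory while the subject remains exposed.

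The subject concerned is foreseeable. Section 1.3.2.4 describes transaminase elevations on ponesimod without any bilirubin increase, so the limb that is checked weekly may stay quiet. Exclusion criterion 13 removes only subjects with ALT or AST at or above 3.0 x ULN at screening, so a subject can enter just below the alert level. At stake is continued dosing in someone who already meets a discontinuation criterion, with no required test to show it until the next full panel.

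**Working it through.** The protocol gives no figure to reproduce. The check has two parts: who stays on drug, and how far apart the required INR values are.

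**Step 1: who stays on drug.** Take confirmed ALT or AST above 3 and up to 5 x ULN, TBL at or below 2 x ULN, INR at or below 1.5, and none of the listed symptoms or eosinophilia.
- The stops for Grade 4, for Grade 3 in specified study-day ranges and for Grade 3 on 5 mg are not met.
- The combined transaminase rules are not met.
- Interruption starts at Grade 3, so it does not apply.

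The subject continues ponesimod under the weekly box. A subject with only a Grade 2 recurrence after re-initiation is in the same position.

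**Step 2: which tests are required meanwhile.**

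| Occasion | Named or required | INR required by the text? |
|---|---|---|
| Scheduled visit (Table 1) | Chemistry panel | Yes |
| Re-initiation visit (8.5.1) | Chemistry panel | Yes |
| 72-hour repeat (5.1.10.3) | The alerted test, not itemised | Unspecified |
| Weekly box (5.1.10.3) | AST, ALT, TBL | No |
| Re-tests after re-initiation (5.1.10.3) | AST, ALT, TBL | No |
| Other unscheduled visit (Table 1, 8.5.2) | Chemistry optional | No |

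**Step 3: interval between required INR values, leaving aside re-initiation visits.**

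Inputs: Core visits every 4 weeks (Table 1). Extension visits at EX-Weeks 4, 8, 12, 16, 20, 24, 36, 48, 60, 72, 84 and 96 (3.2.4). Visit window ±7 days at Weeks 12, 16 and 20 (8.2.4, 8.2.5) and at the extension visits after EX-1 (8.4.2 to 8.4.4). At Weeks 12, 16 and 20, blood chemistry may also be drawn up to 7 days before or after the visit date.

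Formula: longest interval = nominal spacing + allowance at the first visit + allowance at the second visit.

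- Core, nominal: 4 × 7 = 28 days.
- Core, longest (for example Week 16 to Week 20, adding the sampling allowance to the visit window): 28 + (7 + 7) + (7 + 7) = 56 days.
- Extension to EX-Week 24: nominal 28 days; longest 28 + 7 + 7 = 42 days.
- Extension after EX-Week 24: nominal 12 × 7 = 84 days; shortest 84 − 7 − 7 = 70; longest 84 + 7 + 7 = 98 days.

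**Step 4: weekly re-tests falling between required INR values.** At 4-week spacing, 28 / 7 − 1 = 3. At 12-week spacing, 84 / 7 − 1 = 11. Each would supply ALT, AST and TBL for the rule, but not necessarily INR.

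**The case against.** The strongest reply is that the weekly box sets a minimum within a wider net of care. It allows more frequent testing and visits and asks for specialist work-up to be considered. Section 7.3.11.1 sends re-tests to the central laboratory and calls for further analyses as indicated. Alerts reach both investigator and sponsor, the Study Monitoring Committee reviews each subject's toxicity, and 5.1.9 tells the investigator to stop drug when continuing is against the subject's interest. An alert raised at a scheduled visit normally comes with that visit's INR. All of this stands and lowers the risk, but none of it requires an INR at the later re-tests.

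Several stronger readings do not hold:

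- **That the re-tests are incapable of showing INR.** A site may order the full panel, and the laboratory manual, which is not among the documents, may return INR with the re-test kit. The text supports only that INR is not required.
- **That the 72-hour repeat excludes INR.** It is silent. Because the stopping criteria are applied once that repeat confirms the abnormality, reading INR into it is reasonable.
- **That the post-re-initiation re-tests are a separate gap of equal weight.** Re-initiation requires values back at baseline, and the visit requires a chemistry panel. A later rise above 3 x ULN would trigger the alert, the 72-hour repeat and, once confirmed, the weekly box. Correcting those two largely covers it.
- **That the Table 9 alert leaves someone unalerted.** Its thresholds differ slightly from the stop (INR at or above 1.5 x ULN with ALT or AST at or above 3 x ULN). The stand-alone ALT/AST alert already fires, so no subject is missed.
- **That the intervals translate into an average delay.** That would need a distribution for when INR crosses 1.5 and an assumption that nobody orders it during weekly follow-up of a known liver elevation. The documents support neither.

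It is also fair to note that the eosinophilia criterion depends on hematology, which the weekly box does not name either. That is a parallel observation and does not close the INR gap.

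**Conclusion.** The point holds as a gap between a mandatory stop and the tests required to apply it. In a subject kept on ponesimod with isolated confirmed Grade 2 ALT or AST, the INR limb need not be checked between chemistry panels at scheduled or re-initiation visits. The nominal interval is 4 weeks in Core and up to EX-Week 24, then 12 weeks. The upper bounds are 98 days late in the extension and 56 days in Core. The Core bound assumes that the sampling allowance at Weeks 12, 16 and 20 adds to the visit window, as the wording permits. Both are upper limits on a required-test interval, not expected delays.

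The practical size is small. About 30 subjects are planned, only some can enter the extension, and the protocol gives no rate of Grade 2 elevation or of INR rise in this population. Section 1.3.2.4 describes the transaminase rises seen so far as asymptomatic and reversible on discontinuation. The bilirubin, symptom and Grade 3 rules remain in force. This is a worthwhile, inexpensive safety improvement. It does not show that the liver monitoring fails.

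**What to change.** Make two edits in 5.1.10.3:

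1. In the weekly monitoring box, write: *AST, ALT, TBL and INR are re-tested weekly*, keeping the existing provision for more frequent testing.
2. State that the 72-hour repeat includes AST, ALT, TBL and INR.

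Naming INR in the re-tests after re-initiation is optional, for consistency. Leave the stopping threshold, the visit schedule and Table 9 unchanged.

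The cost is a short wording change in an amendment and one extra INR assay on draws already being taken, in the few subjects with an alerted liver elevation.

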5.1.10.4 Immune/infection

Subjects must be prematurely discontinued from ponesimod at any time during the study in the event of an infection requiring discontinuation of treatment per investigator judgment.

In the event of an infection, the subject should be treated as clinically indicated and, if medically appropriate, study drug discontinued at the discretion of the investigator. In case of study drug discontinuation, adequate treatment needs to be provided, and the subject must be monitored until complete resolution of the infection.

If the infection resolves and the benefit/risk balance is considered acceptable for the subject to resume study treatment, ponesimod may be re-initiated at the discretion of the investigator. See Section 5.1.8 for re-initiation procedures.

Given ponesimod effects on lymphocytes, heightened vigilance is required for opportunistic infections, with particular attention to be paid to viral infections. However, investigators and physicians following subjects should also be alert to potential systemic infections caused by fungi and bacteria.

Table 5 highlights opportunistic infections common in patients at least 30 days following HSCT (and relevant for the patient population in this study).

Table 5 Common opportunistic infections in patients at least 30 days post-HSCT

Stage	Infections
Post-engraftment: approximately 30 to 100 days post-transplant	
 • Herpes viruses, especially CMV (Note: CMV causes pneumonia, hepatitis, and colitis and potentiates superinfection with opportunistic pathogens, particularly among patients with active GVHD) • Pneumocystis carinii • Aspergillus
Late phase: approximately 100 days post-transplant	
 • CMV • VZV • EBV-related post-transplant lymphoproliferative disease • CRV • Encapsulated bacteria (e.g., H. influenzae and S. pneumoniae).

Adapted from: CDC 2000

CMV = cytomegalovirus; CRV = community-acquired respiratory viruses; EBV = Epstein-Barr virus; GVHD = graft versus host disease; VZV = varicella zoster virus

If an opportunistic infection should occur despite appropriate and tailored infection prophylaxis and if, in the judgment of the investigator, the opportunistic infection does not respond as expected to anti-infectives, the subject must discontinue ponesimod and must be referred to an expert in infectious diseases for further examination and treatment.

The Centers for Disease Control and Prevention (CDC) recommendations for infection prophylaxis and immunizations for chronic GVHD patients can be obtained at: <http://www.cdc.gov/mmwr/preview/mmwrhtml/rr4910a1.htm>. Suggested prophylaxis [as adapted from Martin 2009] appears in Table 6.

Table 6 Suggested infection prophylaxis in chronic GVHD

Infection or Risk Scenario	Prophylaxis (Comment)
Pneumocystis pneumonia and encapsulated bacterial infections	Antibiotic prophylaxis is strongly recommended for all patients until 6 months after resolution of chronic GVHD and discontinuation of all systemic IS treatment.
Pneumococci and haemophilus influenzae B	Vaccination with conjugate pneumococcal vaccine at 1 year after HSCT is strongly recommended. (Comment: chronic GVHD impairs splenic clearance of encapsulated organisms. Response to unconjugated vaccines is poor in patients at 1 year after HSCT).
Recurrent bacterial infections in patients with serum immunoglobulin G concentrations < 400 mg/dL or deficiencies of IgG2 or IgG4	Intravenous administration of gamma globulin may be indicated.
Patients who are at risk of CMV infection	Virologic surveillance of blood and pre-emptive antiviral therapy should be instituted whenever surveillance tests become positive, before the onset of overt CMV disease. (Comment: if feasible, CMV-seronegative recipients with CMV-seronegative donors should receive screened or leukocyte-depleted blood products).
MMR, and other infections prevented with live virus vaccines	Patients should not be given live virus vaccines such as MMR until at least 1 year after resolution of chronic GVHD and withdrawal of all IS treatment.
VZV	Long-term administration of valacyclovir or acyclovir is recommended to prevent reactivation of VZV in patients previously infected with this virus. The safety and efficacy of VZV vaccination after resolution of chronic GVHD has not yet been determined.
Patients on glucocorticoid treatment: glucocorticoid treatment increases the risk of fungal infections	Prophylactic administration of fluconazole can prevent certain types of candida infections, but this agent is not effective for prevention of invasive mold infections. (Comment: clinical trials will be needed to determine whether newer agents such as itraconazole, voriconazole, or posaconazole can prevent invasive mold infections during glucocorticoid treatment for patients with chronic GVHD).

Adapted from: [Martin 2009]

CMV = cytomegalovirus; GVHD = graft versus host disease; HSCT = hematopoietic stem cell transplantation;

IS = immunosuppressant; MMR = measles, mumps, rubella; VZV = varicella zoster virus.

Confidential

Particular vigilance is required for rare and unusual neurological symptoms, as their recognition is crucial for the early diagnosis of neurotropic herpes virus infections and progressive multifocal leucoencephalopathy (PML), caused by reactivation of John Cunningham virus. Neurological warning signs for PML include major changes in vision, unusual eye movements, loss of balance or coordination, disorientation, and confusion. As there is no known treatment for PML, rapid recognition is essential. Several cases of PML have been reported in patients with GVHD [Focosi 2007].

The thorough physical examination and blood tests on the routine visits should focus on any potential sign of skin, mucosal surface, GI tract, liver, hematological, or other abnormality and organ dysfunction suggesting a potential opportunistic infection.

Subjects should be advised to be pro-active and alert in reporting any unusual neurological symptoms and any signs and symptoms indicative of systemic infections, such as fever, malaise and fatigue [Kappos 2011].

